2.4. Study eligibility criteria

2.4.1. Core inclusion criteria

- Signed written electronic consent
- Confirmed PD clinical diagnosis based on self-report
- A verified diagnosis of depressive disorder, according to adjusted DSM-5 criteria [14].
- Aged 35-85
- Currently using levodopa or a dopamine agonist
- Stable frequency, dosage and use of levodopa, dopamine agonists and antidepressants or other psychopharmacological medication for at least 6 weeks
- Internet access from a computer or tablet.

2.4.2. Core exclusion criteria

- Cognitive impairment as defined by MoCA Blind version scores of <18
- Suicidal thoughts with plan and intent (based on clinical interview)
- Medically unstable
- Currently receiving psychotherapeutic treatment, or in psychotherapy within the last 2 months before inclusion
- History of bipolar or psychotic disorders
- Does not speak Norwegian
- A history of neurosurgery (such as deep brain stimulation)
- No familiarity and/or access to a computer or tablet with camera, or limited internet access

2.5. Sample size and feasibility

A priori power calculations was performed using G*Power 3.1.9.2 [15,16]. Power analysis is based on power calculation for *t*-test, and it serves as a lower bound estimate of power as it applies as long as each patient has at least two measurements. Multiple observations per subject will increase the power and eliminate the impact of possible missing

observations. The study is powered to identify a mean difference in HADS-D score of 1.98 points, with $\alpha = 0.05$, power set to 80%, and a predicted effect size of Cohen's $d = 0.80$. Based on these calculations, the required number of participants is 84 (42 per group). Including $N = 60$ participants per group will allow for up to 30% dropout from the study, while retaining sufficient statistical power. Based on the large effect sizes observed in other RCTs investigating CBT for depression in PD [6–8], we expect the effect size to be larger and the drop out to be lower ($\approx 10\%$). Participants whom decide to leave the study prematurely will not be replaced by new participants, and their data will be included in the main analysis according to an intention-to-treat principle.

There is an estimated 7000 patients with PD in Norway, of whom about 3500 are members of the patient organization the Norwegian PD Association. With a conservative frequency of 30%, depressive symptoms would affect approximately >2000 Norwegian PD patients in general, and >1000 of the members of the Norwegian PD Association. While access to computers and adequate internet bandwidth is largely ubiquitous in a Norwegian setting, familiarity with online platforms and video-conferencing could still limit recruitment for this study. However, a recent nationwide survey using similar data-gathering tools demonstrated that a large proportion of the PD community manages to use the technologies employed in this study [17]. Thus recruitment of $N = 120$ participants for this study is thus considered feasible.

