2.3. Recruitment procedures

A recruitment and information website will be established for the study. As well as being a recruitment portal, this website will also contain instructions on how to complete online self-report measures, and how to use the videoconference system "Join.nhn.no". The study will recruit participants in collaboration with 1) neurological clinics in all four health regions of Norway, and 2) the national user organization for people with PD in Norway (Norwegian PD Association, NPDA). The role of collaborating clinics and the NPDA is to raise awareness of the study, to inform potential participants and direct them to the bespoke study web-page. Neither the clinics nor NPDA will be required to perform any assessment of potential participants.

Potential study participants will be directed to the study website, where they will be informed about the design and goals of the study. Those visiting the website will be informed that participation is voluntary, and that they have the right to withdraw from the study at any time without the risk of repercussions or prejudice. Participants interested in joining the study are then guided to an online platform (on the TSD-platform, see details later in the protocol) to read and sign an informed consent form. After signing an informed consent form, all participants will complete an online screening procedure, consisting of a short, structured questionnaire, and self-report measures for depression and anxiety. The screening procedure includes the following: a) Screening form addressing demographic information, medical history

and current symptoms, and subjective cognitive complaints; and b) Hospital Anxiety and Depression Scale (HADS). A score of >7 on HADS depression items (HADS-D) will be considered a positive screening for depression [11]. This cut-off is in line with previous studies using HADS with PD [12]. After completion of the screening procedure, participants meeting the central *a priori* inclusion criteria (see section 2.4) will be invited to a second screening after one to two weeks. Patients will also be informed that they may use the time until the second screening session to reflect on whether they want to participate in the study.

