Also, due to the online design of this study several additional security precautions will be in place before initiation of the study. These include procedures of how to address acute medical situations, such as suicidal ideation or acute psychosis. For each participants a security card, with emergency contacts, contact information to nearby emergency services, ambulatory mental health services and general practitioner, will be prepared before the initiation of interventions. These data will be gathered during the second screening/baseline assessment. In case of increased suicidal ideation during the course of treatment, clinicians will follow local clinical guidelines for increased suicidal ideation. Clinicians are free to admit patients to acute outpatient or inpatient care in case of acute suicidal ideation. Participants with acute suicidal ideation will be excluded from the study.

3. Analysis plan

All analyses in this project will be performed using IBM SPSS Statistics version 26.0.0.1 or R 4.2.1, or more recent versions if available. An alpha-level of 0.05 will be used to indicate statistical significance. Descriptive statistics will be summarized using means, median, standard

deviations and ranges for numerical variables, and frequencies and percentages for categorical variables. Relevant univariate and multivariate analytic strategies will be used to test hypotheses h^i - h^{viii} .

For aim 1 (h^i - h^{iii}), linear mixed model analysis (LMM) with maximum likelihood estimation, based on an intent-to-treat protocol, will be used to gauge the between-group differences from baseline to the 14 week follow up. LMM will limit the impact of type 1 errors, and fully use the available data (in case of missing data). A random intercept for each participant and random slope will be included if they enhanced the model fit (evaluated using Akaike’s information criteria and Schwarz’s Bayesian criterion). In these analyses, a sum score from the primary and secondary outcomes will be used as dependent variables, and with significant covariates including treatment group, age, gender, duration of PD, and medication use. Medication use will be converted to levodopa equivalent dosages, using previously described procedures [18]. This analysis will be repeated using a per-protocol approach, where only completers (completed all core sessions) are included. Effect sizes will be calculated using Cohen’s d , with pooled pre- and post-SD adjustment for sample size.

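### Section 2.5 calls the t-test power a lower bound given two measurements per patient, but two measurements alone do not ensure this for the baseline-to-week-14 contrast

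*Protocol*

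**What the plan says.** Protocol section 2.5 sets out to "identify a mean difference in HADS-D score of 1.98 points, with $\alpha = 0.05$, power set to 80" percent, with a Cohen's d of 0.80, and concludes that "the required number of participants is 84 (42 per group"). Sixty per group are to be recruited, to allow for 30% dropout. The calculation is for a t-test, and the section says of it that "it serves as a lower bound estimate of power as it applies as long as each patient has at least two measurements". The next sentence says that several observations per subject make power larger. No between-visit correlation is given, and the section does not say whether the 1.98 points and d = 0.80 rest on the SD of HADS-D scores or of changes in score.

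Protocol section 3 analyses aim 1 with a linear mixed model used to "gauge the between-group differences from baseline to the 14 week follow up". It names a random intercept, a random slope if fit improves, and covariates that include treatment group. It states no group-by-time term, no adjustment for the baseline score and no common baseline mean. Reported effect sizes are to be standardised by a pooled pre- and post-treatment SD.

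**The concern.** The only condition attached to the lower bound is that "it applies as long as each patient has at least two measurements". Whether a second measurement helps depends on how the model uses it. A baseline used as a covariate, or given a common mean across arms, can only reduce the residual variance. A baseline that is simply subtracted adds its own noise, and at low correlation this outweighs what it removes. The aim 1 wording, a between-group difference from one visit to the other, can naturally be read as the second case.

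At stake is the reliability of an assurance. A reader of section 2.5 would take the t-test figure as a floor that the mixed model can only improve on. Under one plausible reading of section 3 it is not a floor, and under another the second visit brings no gain.

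**Working it through.** **Inputs.** From section 2.5: difference 1.98, d = 0.80, alpha 0.05, power 80%, 42 per group needed, 60 recruited. Implied SD = 1.98 / 0.80 = 2.475. Assumptions: two-sided test (sidedness is not stated), equal allocation, complete data at both visits, and rho varied because the protocol gives no value.

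**The plan's own figure.** Exact noncentral t with df = 2n − 2 and noncentrality d·√(n/2):
- d = 0.80 and 80% power need 26 per group, not 42.
- At 42 per group and d = 0.80, the noncentrality is 0.80·√21 = 3.67 and power is 95.2%.
- 42 per group gives 80% power at d = 0.619, an SD of about 1.98 / 0.619 = 3.2.

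So d, power and N in section 2.5 do not agree. That is a separate defect. It matters here because it leaves two possible reference points.

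**Variance of each contrast, relative to a week-14 t-test on scores (equal SDs).**
- Week-14 scores: σ², factor 1.
- Unconstrained difference in change: σ² + σ² − 2ρσ² = 2σ²(1 − ρ), factor 2(1 − ρ). This exceeds 1 exactly when ρ < 0.5.
- Week 14 conditioned on baseline, or with a common baseline mean: σ²(1 − ρ²), factor 1 − ρ², never above 1.

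With unequal SDs the change contrast is the noisier one when ρ < SD(baseline) / (2·SD(week 14)). At an SD ratio of 0.8 the threshold is 0.4.

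**Power at 42 per group, d = 0.80 on the score SD.** The effective d for change is 0.80 / √(2(1 − ρ)); for the conditioned contrast it is 0.80 / √(1 − ρ²).

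| rho | d, change | Change contrast | Week-14 t-test | Conditioned on baseline |
|---|---|---|---|---|
| 0 | 0.566 | 72.6% | 95.2% | 95.2% |
| 0.2 | 0.632 | 81.7% | 95.2% | 95.9% |
| 0.3 | 0.676 | 86.5% | 95.2% | 96.7% |
| 0.4 | 0.730 | 91.1% | 95.2% | 97.7% |
| 0.5 | 0.800 | 95.2% | 95.2% | 98.7% |
| 0.6 | 0.894 | 98.2% | 95.2% | 99.5% |

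Simulation of the t-test and change columns (20,000 trials per setting) agreed within about half a percentage point.

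**Where the 80% target is lost at d = 0.80.** At 42 per group the change contrast reaches 80% at rho of about 0.16. At 60 per group it has 86.7% even at rho = 0, so the target holds for every rho of 0 or more.

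**If d = 0.80 is on the SD of change.** The t-test is then itself a test of change. With two visits the mixed-model change contrast is the same comparison and has the same power at every rho.

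**If 42 per group is the true 80% design point (d = 0.619).** The change contrast has 60%, 66% and 72% at rho 0.2, 0.3 and 0.4, and the conditioned contrast has 82%, 84% and 86%. These figures depend on how the mismatch of d, power and N is resolved.

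**The case against.** The strongest reply is that section 3 does not commit to a change contrast. A mixed model that adjusts for baseline, or assumes a common baseline mean, makes the lower bound true apart from a small loss of degrees of freedom, and such terms are often left to a statistical analysis plan. This stands as a limit on the point: the protocol does not fix a model that breaks the bound. It does not rescue section 2.5, which asserts the bound on the sole condition of two measurements.

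A second reply is that requiring two measurements suggests a t-test on change, since a week-14 t-test needs only one. This is possible. Equality would satisfy a lower bound, so the claim would not be false, but the second visit would then add no power to the aim 1 contrast. The pooled pre- and post-treatment SD in section 3 points towards a score SD, but it governs the reported effect size and is not tied to the planning value.

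Two stronger readings are tempting. A reader might infer that the trial is underpowered, with power of 60 to 72%. The documents do not support that from this point: those figures need d of about 0.62, which appears nowhere in the protocol, and at the stated d = 0.80 power stays above 80% unless rho is below about 0.16.

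A reader might also infer that selecting patients because "A score of >7 on HADS depression items (HADS-D) will be considered a positive screening for depression" forces rho below 0.5. The direction is plausible, but the protocol gives no HADS-D mean, SD or correlation. The cut-off also applies at the first online screening, is not in the section 2.4.1 inclusion list, and HADS is measured again at baseline. The effect on rho cannot be settled from the document, and the point does not rely on it.

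**Conclusion.** The lower-bound statement is not justified by the condition attached to it. For an unconstrained change contrast with d on the score SD and equal SDs, power is below the t-test's for rho under 0.5, by 13.5, 8.7 and 4.1 percentage points at rho 0.2, 0.3 and 0.4 with 42 per group (95.2% less 81.7%, 86.5% and 91.1%). With d on the SD of change there is no shortfall and no gain. With baseline conditioned on, the statement is right. The protocol does not say which case applies.

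This is a defect of wording and specification; it does not show that the sample size is too small. The sizes assume a two-sided test, complete data at both visits and the range of rho shown.

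**What to change.** In section 2.5, state whether 1.98 / 0.80 uses the SD of HADS-D scores or of changes. In section 3, specify that the aim 1 contrast is the week-14 group difference conditioned on baseline HADS-D, or estimated with a common baseline mean for the two arms. With d on the score SD, the lower-bound statement can then stay, tied to that contrast and subject to a small loss of degrees of freedom.

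If that contrast is not adopted, remove the lower-bound claim and the claim that repeated observations raise power, and give power for the contrast actually analysed over a range of rho, for example 0.2 to 0.6.

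The cost is a few sentences. Baseline HADS-D is already collected before allocation, so no visit, measure or sample size changes. The mismatch of d, power and N should be reconciled at the same time, because any power figure quoted depends on it.

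### The sample-size inputs do not give the stated N: d = 0.80 at 80% power and alpha 0.05 (two-sided assumed) needs 26 per group, whereas 42 per group corresponds to 95% power

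*Protocol*

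**What the plan says.** Protocol section 2.5 (Sample size and feasibility) reports a G*Power calculation. On the method it says: "Power analysis is based on power calculation for *t*-test". The inputs are alpha 0.05, 80% power and a predicted Cohen's d of 0.80, and the target difference is given in scale points: "The study is powered to identify a mean difference in HADS-D score of 1.98 points". The result follows directly: "Based on these calculations, the required number of participants is 84 (42 per group".

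Dropout is then added. Sixty "participants per group will allow for up to 30% dropout from the study, while retaining sufficient statistical power". The same section expects the true effect to be larger than assumed and dropout to be nearer 10%.

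Neither the SD nor the sidedness of the test is stated. Section 3 (Analysis plan) uses the same significance level and mentions no adjustment: "An alpha-level of 0.05 will be used to indicate statistical significance".

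**The concern.** A two-group t-test with d = 0.80 and 80% power is a standard case whose answer lies in the mid-twenties per group, so 42 is conspicuous. The protocol presents 42 as the outcome of the listed inputs, so at least one of the listed figures must be misstated.

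The possible corrections describe different trials. If the power figure is wrong, the trial has about 95% power for d = 0.80 even after 30% dropout. If d is wrong, it has 80% power for d = 0.62 after 30% dropout, with nothing to spare. The claim that power stays sufficient at 30% dropout is comfortable on the first reading and only just met on the second. With no SD stated, the reader cannot decide between them, and any later interpretation of a null or borderline HADS-D result would draw on this paragraph.

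**Working it through.** **Inputs (section 2.5):** two-sample t-test, equal groups; alpha 0.05; power 80%; d = 0.80; difference 1.98 points; 42 per group required; 60 per group enrolled; dropout up to 30%. **Assumption:** two-sided test; one-sided is checked below.

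**Formula.** With n per group, df = 2n − 2 and noncentrality δ = d × √(n/2). Power is the probability that a noncentral t variable with that df and δ falls beyond ±t(0.975, df).

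**1. Trying to reproduce the stated figure at d = 0.80**

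| n per group | δ | critical t | power |
|---|---|---|---|
| 25 | 0.80 × √12.5 = 2.828 | 2.011 | 0.791 |
| 26 | 0.80 × √13 = 2.884 | 2.009 | **0.807** |
| 41 | 0.80 × √20.5 = 3.622 | 1.990 | 0.947 |
| 42 | 0.80 × √21 = 3.666 | 1.989 | **0.952** |
| 54 | 0.80 × √27 = 4.157 | 1.983 | 0.985 |
| 60 | 0.80 × √30 = 4.382 | 1.980 | 0.991 |

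The first n to reach 80% is 26 (52 in total). The normal approximation agrees: 2 × (1.960 + 0.842)² / 0.80² = 24.5, so 25. The first n to reach 95% is 42 (84 in total). The stated figure is therefore 42/26 = 1.62 times what the stated inputs require.

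**2. Other readings at d = 0.80 and 80% power**

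- One-sided, alpha 0.05: 21 per group.
- Wilcoxon-Mann-Whitney, with efficiency 3/π or 0.864: 28 or 31 per group.
- Paired t-test: 15 in total.
- Two-sided alpha 0.05/3, for the three primary outcomes in Table 2: 35 per group.
- Two-sided alpha 0.01: 39 per group.
- Two-sided alpha 0.05/8: 42 per group. This matches, but the protocol states 0.05 in both places and no adjustment.

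**3. Holding 80% power and 42 per group fixed.** Solving for d gives 0.619, which is 0.18 below the stated 0.80.

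**4. Implied SD.** From the stated d: 1.98 / 0.80 = 2.475. From 42 per group at 80% power: 1.98 / 0.619 = 3.20.

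**5. Dropout.** 60 × 0.70 = 42, so this step is consistent. At the expected 10%, 60 × 0.90 = 54.

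**6. Power for 1.98 points by SD.** The first row is the SD implied by the stated d. The second is the SD implied by 42 per group at 80% power. The rest are assumed, to show the range.

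| SD | d | 42 per group | 54 per group |
|---|---|---|---|
| 2.475 | 0.80 | 95% | 98% |
| 3.2 | 0.62 | 80% | 89% |
| 3.0 | 0.66 | 85% | 92% |
| 3.5 | 0.57 | 73% | 83% |
| 4.0 | 0.50 | 61% | 72% |

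The detectable d at 80% power is 0.62 with 42 per group and 0.54 with 54.

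**The case against.** The best defence accepts the arithmetic and disputes its weight.

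- **No harm on the stated inputs.** If d = 0.80 is right, the trial has about 95% power at 42 per group and 98% at 54. If d is the wrong figure, 42 per group still gives 80% power for d = 0.62. N need not change on either reading. This stands: the error does not show that the trial is underpowered.
- **The SD is not free.** The stated pair of 1.98 points and d = 0.80 fixes it at 2.475, and nothing in the protocol supports 3.5 or 4.0. This stands in part. Those values are illustrations only. But 80% power with 42 per group fixes the SD at about 3.20, so the paragraph implies two different SDs.
- **Power need not be the misstated input.** Eight hypotheses are listed in section 1.1, and alpha 0.05/8 also leads to 42 per group. It is right that the match with 95% power does not prove where the slip lies. However, sections 2.5 and 3 both state 0.05, so this route has no support in the text.
- **Sidedness is assumed.** True, but a one-sided test needs 21 per group and widens the gap.
- **The t-test is described as conservative because repeated measurements add power.** That would lower the required number, so it cannot explain 42 in place of 26.

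**Conclusion.** The concern holds. The stated inputs give 26 per group (two-sided, assumed) or 21 (one-sided), not 42. Seen one at a time, the required n is overstated by 62%, or the power is understated by 15 percentage points, or d is overstated by 0.18. The protocol does not show which. An unstated smaller alpha would be a further explanation, but it contradicts the text.

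This is an error in the central justification of the sample size, not a demonstration that 120 patients are too few. On d = 0.80 the trial exceeds its stated power. How much margin it has for 1.98 points depends on whether the SD is 2.475, as d implies, or about 3.20, as 80% power with 42 per group implies. The sponsor needs to settle that.

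**What to change.** Keep N = 120 and rewrite the calculation in section 2.5 so that power, d, the 1.98-point difference, SD, alpha, sidedness and N agree. Wording that reproduces, for a two-sided alpha of 0.05:

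> With 42 evaluable participants per group (30% dropout) the trial has 95% power for d = 0.80, which is 1.98 HADS-D points if the SD is 2.475, or 80% power for d = 0.62. With 54 per group (10% dropout) it has 98% power for d = 0.80, or 80% power for d = 0.54.

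State the SD and its source, and where the 1.98-point difference comes from. If the SD is uncertain, a short table of power for 1.98 points at SDs of 2.5, 3.0, 3.5 and 4.0 would show the margin; this is useful but secondary to the reconciliation. If a smaller alpha was used in the original calculation, say so and bring section 3 into line.

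The cost is one paragraph. Neither the number recruited nor the conduct of the trial changes.

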2.6. Randomization, allocation concealment and blinding

After completion of the baseline examination, participants will be randomly assigned to either Arm A (CBT followed by TAU) or Arm B (TAU followed by CBT) using a randomized block design with 20 blocks

of six participants. For participants randomized to arm A, the eCBT intervention will be initiated in short succession of the baseline visit, with 10 treatment sessions to be conducted over the next 13 weeks. The allocation key will also be stored on an access restricted research server, only accessible by key personnel.

Due to the nature of the intervention, neither patients nor therapists can be blinded to the intervention or treatment allocation. However, all video-based assessments will be performed by study personnel blinded to the treatment allocation, in order to limit the risk of bias. Participants will not be allowed to share this information during the follow up visits. During the start of each assessment, the study personnel will remind the participant that they should not share whether they have received the intervention or not. Study personnel schedule assessments with the participants independently of the clinical personnel.

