2.2. Study design

This study is an online, randomized, delayed start trial of the effectiveness of eCBT for PD patients with depressive symptoms. N = 120 PD patients with depressive symptoms will be recruited from outpatient clinics and via self-referral in Norway, and randomized into two arms: (A) immediate 10-weeks eCBT with concurrent TAU and (B) a delayed start (14 weeks) of eCBT with TAU alone. Patients will be assessed at baseline before allocation to a specific treatment arm, with follow-up evaluations after 14, 28 and 42 weeks. See Fig. 1 for the study flow.

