During the second screening process, participants will undergo a more comprehensive evaluation of their medical history, medication use, clinical status, cognitive functioning, and severity of neuropsychiatric symptoms. This screening will be performed by a trained study nurse over "Join.nhn.no". After the second screening, patient records will be evaluated by an interdisciplinary team (nurse and senior consultant clinical psychologist) against the criteria for major depressive disorder (MDD). The diagnosis of MDD will be assessed using the provisional diagnostic criteria for depression in PD and the MDD criteria from the Diagnostic and Statistical Manual for Mental Disorders, 5th edition [13,14]. Participants will be considered for inclusion in the study according to the core inclusion and exclusion criteria (see 2.4 study eligibility criteria). Included patients will be trained in the use of the TSD-platform while completing a set of self-report measures as part of their baseline assessment. Excluded patients will be referred on to appropriate treatment services near their area of living. For all included participants, information will be passed on to the treating neurologist and general practitioner, detailing the aims of the study, information of diagnostic assessments of PD, and information of medication limitations during the trial.

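### A single fixed, published block size of six makes an expected quarter of assignments certain to anyone who can follow earlier ones in order

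*Protocol*

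**What the plan says.** Section 2.6 of the protocol assigns participants to Arm A or Arm B after baseline, "using a randomized block design with 20 blocks" "of six participants". Section 2.2 gives the total ("N = 120 PD patients with depressive symptoms will be recruited") and section 2.5 the split ("Including $N = 60$ participants per group"). No stratification factor, site-level list or second block size appears anywhere.

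On blinding, section 2.6 states that "neither patients nor therapists can be blinded to the intervention or treatment allocation", but that "all video-based assessments will be performed by study personnel blinded to the treatment allocation". It adds that assessments are scheduled independently of the clinical staff. On concealment, the one measure described is this: "The allocation key will also be stored on an access restricted research server, only accessible by key personnel".

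Arm A starts treatment shortly after the baseline visit (section 2.6). Arm B starts after its 14-week assessment (section 2.7). Before randomisation, after the second screening, "patient records will be evaluated by an interdisciplinary team (nurse and senior consultant clinical psychologist") against the depression criteria (section 2.3). The trial therapists are also clinical psychologists (section 2.7).

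**The concern.** Permuted blocks keep the arms balanced by forcing the last places of each block. When every block has the same size and that size is in print, anyone who knows the earlier assignments in order knows where each block ends. That person can tell when the next place is forced, without opening the key.

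In this trial assignments become visible to treatment staff as they are acted on, because therapists are unblinded and one arm starts promptly. What is at stake is concealment at entry. Some eligibility criteria need judgement: the depressive-disorder diagnosis, medical stability, and suicidality at clinical interview (section 2.4). If the person judging them could foresee the arm, the decision to include could depend on it.

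**Working it through.** **Inputs**
- Blocks: 20, of size 6 (section 2.6).
- Total 120 (section 2.2); 60 per group (section 2.5).
- Split within a block: 3 A and 3 B. This is inferred from the equal groups and is not stated.

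**The plan's own figure.** 20 × 6 = 120, so the fixed blocks account for the whole planned sample and leave no room for other sizes.

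**Certain assignments with fixed blocks of six.** There are C(6,3) = 20 equally likely orderings. A place is certain once one arm has used its three places.
- Places 1 to 3: never certain.
- Place 4: certain if the first three are all the same arm, 2/20 = 10%.
- Place 5: certain if one arm has three of the first four, 8/20 = 40%.
- Place 6: always certain, 100%.

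Expected number per block = 0.10 + 0.40 + 1.00 = 1.5, and 1.5/6 = 25%. Over the trial, 20 × 1.5 = 30 of 120. The closed form for block size 2m is 2m/(m+1) per block, a share of 1/(m+1); with m = 3 it gives 1.5 and 25%.

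The number certain in one block is 1 in 12 orderings, 2 in 6 and 3 in 2: (12×1 + 6×2 + 2×3)/20 = 1.5. The minimum is one per block, so at least 20 × 1 = 20 of 120 are certain in any list.

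**Guessing rate.** Always guess the arm with more places left, and toss a coin when they are equal. The success rates by place are 0.5, 0.6, 0.6, 0.7, 0.7 and 1.0. They sum to 4.1, and 4.1/6 = 68.3%, against 50% by chance.

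**Alternatives.** For varying sizes, lists of 120 were simulated with equally likely sizes. The observer was assumed to know the set of sizes and all past assignments, but not the order of the sizes.

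| Blocks | Certain | Guessed correctly |
|---|---|---|
| Fixed 6 | 25% | 68% |
| Fixed 8 | 20% | 67% |
| Fixed 10 | 16.7% | 65% |
| Varying 4, 6 | about 5% | about 69% |
| Varying 4, 6, 8 | about 2% | about 68% |

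Varying the size removes most of the certainty. It does not lower the general guessing rate.

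**The case against.** The strongest reply is that predictability on paper needs a person who can use it, and the protocol names none.

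- Section 2.6 separates assessment scheduling from the clinical staff, and section 2.8 has blinded nurses do the baseline evaluation. This stands. A reader might infer that therapists could time baseline visits to suit an expected arm; the protocol's own arrangements speak against it.
- There are several therapists, and an Arm B patient reaches one only after 14 weeks. A therapist is therefore sure to see only their own started patients, not the ordered trial-wide sequence. This stands too, and it is why the 25% applies only to someone who can follow assignments in order. Those with access to the key can read the list itself, so block size makes no difference to them.
- Sharing a profession with the therapists does not show that the psychologist judging eligibility also treats. Correct: the protocol is silent here, and overlap is only a possibility.
- Eligibility is partly constrained by a HADS-D cut-off and by formal diagnostic criteria, and assignment follows a completed baseline. This narrows the opening but does not close it, since the decision to include comes before assignment.
- Assessors are blinded, and participants are reminded not to disclose their treatment. A reader might infer that assessors could work out allocations from the block structure. That would need the randomisation order plus several accidental disclosures, and nothing in the protocol suggests either.

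None of this makes the next assignment unpredictable. The safeguards protect outcome rating and limit who can act; the sequence itself stays as open as the block size makes it.

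**Conclusion.** The point holds as a minor weakness of design, not as a contradiction or evidence of bias. One disclosed block size of six makes an expected 25% of assignments (about 30 of 120, never fewer than 20) certain to anyone who can follow the earlier ones in order. Limiting access to the key does not change that. The figure assumes 3:3 blocks and one list for the whole trial; both are inferred, from the 60 per group and from the absence of any strata or site lists.

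Two stronger readings are tempting and are not supported. A reader might turn the 68.3% guessing rate into a bias in HADS-D points. That would need one person with complete ordered knowledge who steers every enrolment, plus a size of shift that the protocol gives no basis for. A reader might also infer that any such bias would be beyond repair. The mixed model in section 3 estimates group differences from baseline to 14 weeks, so a shift in the entry score would be at least partly accounted for. Selection on unmeasured prognosis is what could remain.

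**What to change.** For participants not yet randomised, generate a new list with randomly varying block sizes, for example 4, 6 and 8. Do not disclose the sizes to staff who screen, treat or assess; the protocol need say only that sizes vary. Add a sentence to section 2.3 or 2.6 stating that whoever judges eligibility does not treat in the trial and does not see past allocations.

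This cuts certain assignments from 25% to about 2% with sizes 4, 6 and 8 (about 5% with 4 and 6), even if the set of sizes leaks. It leaves the guessing rate at about 68–69%, so the sentence on separation of roles matters as much as the new list.

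The cost is one new list, a short amendment and a slight imbalance if recruitment ends inside a block. For a full list of 120 with blocks of at most 8, the arms can differ by at most 4 participants, that is 62 against 58. The variance of a difference in means then rises by the factor (1/62 + 1/58)/(2/60) = 1.001, which is negligible. Replacing the list in the middle of a block of six could add a difference of up to 3. No clinical procedure changes.
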